7.0 Protocol Treatment

7.1 Treatment Schedule

Agent	Dose Level	Route	Day
Ponatinib	45mg once daily	PO	Days 1-28

- 7.2 For this protocol, the patient must return to the consenting institution for evaluation at least every 28 days (+/- 2 days) during treatment (Active Monitoring Phase).
- 7.3 Patients should receive low-dose aspirin (e.g. 81mg/day), as prophylaxis against arterial thrombotic events, if not contraindicated.
- 7.4 Patients should receive treatment with a statin, as prophylaxis against arterial thrombotic events, if not contraindicated. Atorvastation, 10-20 mg per day, is suggested.

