8.1 Dose Levels (Based on Adverse Events in Tables 8.2)

Dose Level	Ponatinib
0*	45mg PO once daily
-1	30mg PO once daily
-2	15mg PO once daily

*Dose level 0 refers to the starting dose.

8.2

→ → *Use the NCI Common Terminology Criteria for Adverse Events (CTCAE) version 4.0* unless otherwise specified* ← ←

CTCAE System/Organ/Class (SOC)	ADVERSE EVENT	AGENT	ACTION**
BASED ON INTERVAL ADVERSE EVENT			
Investigations	Neutrophil count decreased ≥ Grade 3	Ponatinib	Omit ponatinib Resume at 45 mg after recovery to ≤ grade 1 Recurrence at 45 mg: Omit ponatinib Resume at 30 mg after recovery to ≤ grade 1 Recurrence at 30 mg: Omit ponatinib Resume at 15 mg after recovery to ≤ grade 1 Recurrence at 15 mg: Discontinue ponatinib

→ → Use the NCI Common Terminology Criteria for Adverse Events (CTCAE) version 4.0* unless otherwise specified ← ←			
CTCAE System/Organ/Class (SOC)	ADVERSE EVENT	AGENT	ACTION**
	Platelet count decreased \geq Grade 3		
Omit ponatinib Resume at 45 mg after recovery to \leq grade 1
 
Recurrence at 45 mg: Omit ponatinib Resume at 30 mg after recovery to \leq grade 1
 
Recurrence at 30 mg: Omit ponatinib Resume at 15 mg after recovery to \leq grade 1
 
Recurrence at 15 mg: Discontinue ponatinib

	Serum amylase increased \geq Grade 3 with no radiographic findings	Ponatinib	
Omit ponatinib Resume at 45 mg after recovery to \leq grade 1
 
Recurrence at 45 mg: Omit ponatinib Resume at 30 mg after recovery to \leq grade 1
 
Recurrence at 30 mg: Omit ponatinib Resume at 15 mg after recovery to \leq grade 1
 
Recurrence at 15 mg: Discontinue ponatinib

	Serum amylase increased \geq Grade 3 with radiographic findings or Grade 4	Ponatinib	
Omit ponatinib Repeat imaging according to clinical care After resolution by imaging, resume at 30 mg after recovery to \leq grade 1
 
Recurrence at 30 mg: Repeat above Resume at 15 mg after recovery to \leq grade 1
 
Recurrence at 15 mg: Discontinue ponatinib

→ → Use the NCI Common Terminology Criteria for Adverse Events (CTCAE) version 4.0* unless otherwise specified ← ←			
CTCAE System/Organ/Class (SOC)	ADVERSE EVENT	AGENT	ACTION**
	Alanine aminotransferase increased (ALT) and/or Aspartate aminotransferase increased (AST) ≥ Grade 3	Ponatinib	Omit ponatinib Resume at 30 mg after recovery to ≤ grade 1 Recurrence at 30 mg: Omit ponatinib Resume at 15 mg after recovery to ≤ grade 1 Recurrence at 15 mg: Discontinue ponatinib

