Skin and subcutaneous tissue disorders	Rash maculo-papular ≥ Grade 2 despite optimal symptomatic therapy	Ponatinib	Omit ponatinib Resume at 45 mg after recovery to ≤ grade 1 Recurrence at 45 mg: Omit ponatinib Resume at 30 mg after recovery to ≤ grade 1 Recurrence at 30 mg: Omit ponatinib Resume at 15 mg after recovery to ≤ grade 1 Recurrence at 15 mg: Discontinue ponatinib
	Rash maculo-papular ≥ Grade 3 despite optimal symptomatic therapy		Omit ponatinib Resume at 30 mg after recovery to ≤ grade 1 Recurrence at 30 mg: Omit ponatinib Resume at 15 mg after recovery to ≤ grade 1 Recurrence at 15 mg: Discontinue ponatinib
Vascular Disorders			
	Thromboembolic event ≥ Grade 1		Discontinue ponatinib

→ → Use the NCI Common Terminology Criteria for Adverse Events (CTCAE) version 4.0* unless otherwise specified ← ←			
CTCAE System/Organ/Class (SOC)	ADVERSE EVENT	AGENT	ACTION**
	Hypertension Grade 2 or 3		
Antihypertensive medication should be initiated or optimized to achieve target blood pressure before interruption or dose reduction of the study treatment at the discretion of the investigator. If hypertension is persistent despite adequate anti-HTN therapy including titration of anti-HTN medication or introduction of additional anti-HTN medications, dose interruption and reduction is recommended according to the below guidelines:
 
Hold ponatinib Resume at 30 mg after recovery to ≤ grade 1
 
Recurrence at 30 mg Omit ponatinib Resume at 15 mg after recovery to ≤ grade 1
 
Recurrence at 15 mg Discontinue ponatinib

	Hypertension ≥ Grade 4	Ponatinib	
Omit ponatinib Resume at 30 mg after recovery to ≤ grade 1
 
Recurrence at 30 mg Omit ponatinib Resume at 15 mg after recovery to ≤ grade 1
 
Recurrence at 15 mg Discontinue ponatinib

Injury, poisoning and procedural complications	Wound complication ≥ Grade 2	Ponatinib	See section 8.47 for guidance
General disorders and administrative site conditions	Edema limbs ≥ Grade 2	Ponatinib	See section 8.45 for guidance
Eye Disorders	Eye Disorders – Other	Ponatinib	See section 8.44 for guidance

→ → Use the NCI Common Terminology Criteria for Adverse Events (CTCAE) version 4.0* unless otherwise specified ← ←

CTCAE System/Organ/Class (SOC)	ADVERSE EVENT	AGENT	ACTION**

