Other Non-Hematologic events	≥ Grade 3	Ponatinib	Omit drug and follow patient at least weekly until adverse event has resolved to grade ≤ 2, restart agent at next lower dose level. See sections 8.41 through 8.47 for guidance on other non-hematologic events

* Located at http://ctep.cancer.gov/protocolDevelopment/electronic_applications.ctc.htm

** Use the following to describe actions in the Action column:

- Omit = Treatment is not given for the day/days that are omitted and will not be made up, but treatment may resume once the adverse event has resolved as mandated in Table 8.2. For example, if treatment is omitted on Day 8, but the adverse event has resolved by Day 15, treatment may resume on Day 15.
- Hold/Delay = Treatment can be made up as part of this cycle
- Discontinue = Treatment is totally stopped

NOTE: If the patient experiences a significant adverse event requiring a dose reduction at the start of the next cycle, then the dose will remain lowered for that entire subsequent cycle. If that cycle is completed with no further adverse events >Grade 2, then the dose may be increased, at the investigator's discretion, one level at a time, in the following cycles.

NOTE: Adverse events requiring a dose-reduction step for any or all drugs beyond the two dose-reduction steps (levels -1 and -2) will be at the discretion of the treating physician, if the decision is made for the patient to be kept on study. These dose reductions must be clearly recorded in reported clinical data.

- 8.3 A new course of treatment may begin on the scheduled Day 1 of a new cycle if:
- The ANC is $\geq 1500/\mu\text{L}$;
 - The platelet count is $\geq 75,000/\mu\text{L}$;
 - Any other Ponatinib related adverse event that may have occurred has resolved to \leq Grade 1 or baseline severity.

If these conditions are not met on scheduled Day 1 of a new cycle, the subject will be evaluated at least weekly and the new cycle of treatment will not be initiated until the adverse event has resolved as described above.

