When therapy is resumed it will be considered day one of this new cycle. If Ponatinib was halted during the previous cycle and was restarted with a one-level dose reduction without requiring an interruption for the remainder of the cycle, then that reduced dose level will be initiated on Day 1 of the new cycle. **If ponatinib was omitted for the remainder of the previous cycle or if the new cycle is delayed due to adverse event newly encountered on the scheduled Day 1**, then the scheduled cycle will be started with a one-level dose reduction. If the study drug cannot be restarted within 28 days of the

scheduled Day 1 of a given cycle, the patient will be removed from study treatment and will proceed to event monitoring.

8.4 Additional adverse event guidance:

8.41 Hepatotoxicity: Iclusig can cause hepatotoxicity, including liver failure and death. Fulminant hepatic failure leading to death occurred in an Iclusig-treated patient within one week of starting Iclusig. Two additional fatal cases of acute liver failure also occurred. The fatal cases occurred in patients with blast phase CML (BP-CML) or Philadelphia chromosome positive acute lymphoblastic leukemia (Ph+ ALL). Severe hepatotoxicity occurred in all disease cohorts. Iclusig treatment may result in elevation in ALT, AST, or both. Monitor liver function tests at baseline, then at least monthly or as clinically indicated. Interrupt, reduce, or discontinue Iclusig as clinically indicated.

8.42 Pancreatitis: Clinical pancreatitis occurred in 6% (28/449) of patients (5%, grade 3) treated with Iclusig. Pancreatitis resulted in discontinuation or treatment interruption in 6% of patients (25/449). The incidence of treatment-emergent lipase elevation was 41%. Check serum lipase every 2 weeks for the first 2 months and then monthly thereafter or as clinically indicated. Consider additional serum lipase monitoring in patients with a history of pancreatitis or alcohol abuse. Dose interruption or reduction may be required. In cases where lipase elevations are accompanied by abdominal symptoms, interrupt treatment with Iclusig and evaluate patients for pancreatitis. Do not consider restarting Iclusig until patients have complete resolution of symptoms and lipase levels are less than 1.5 x ULN.

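### Section 8.3 and Table 8.2 contradict each other on restart dose in six first-event rows and on recovery grade in one, and nothing says which governs

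*Combined protocol and SAP*

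**What the plan says.** Treatment starts at "45mg once daily" in 28-day cycles (Section 7.1). Two places then govern what follows an interruption.

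**Table 8.2** works by type of event. For a first Grade 3 or higher fall in neutrophils it says "Omit ponatinib Resume at 45 mg after recovery to ≤ grade 1". For a first Grade 3 or higher rise in ALT or AST it says "Omit ponatinib Resume at 30 mg after recovery to ≤ grade 1". The Other Non-Hematologic events row says "Omit drug and follow patient at least weekly until adverse event has resolved to grade ≤ 2, restart agent at next lower dose level". For Grade 2 or 3 hypertension it says "Antihypertensive medication should be initiated or optimized to achieve target blood pressure before interruption or dose reduction of the study treatment", and leaves this to the investigator. The definition of Omit under the table lets dosing resume once the event has resolved to the level that the table sets.

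**Section 8.3** works by cycle boundary. A new cycle may start only if neutrophils and platelets meet stated counts and "Any other Ponatinib related adverse event that may have occurred has resolved to" Grade 1 or lower, or baseline severity. If drug stayed off to the end of the previous cycle, or Day 1 is delayed by an event first met that day, "the scheduled cycle will be started with a one-level dose reduction". A patient who still cannot restart 28 days after the scheduled Day 1 leaves study treatment for event monitoring.

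The only tie-break is in Section 8.0. It tells sites to apply the greatest reduction when several adverse events occur together.

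**The concern.** When an interruption runs up to the next Day 1, both texts apply to the same patient. In some rows they give different instructions, and a site cannot follow both. The Section 8.0 tie-break does not help, because it chooses between events, not between two rules for one event.

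The stake in the dose conflict is one dose level. In the recovery-grade conflict it is whether the patient stays on treatment. That bears on the primary endpoint, since stable disease counts as clinical benefit only if it lasts 4 or more cycles (Section 16.11). A removed patient also moves from imaging every 8 weeks (Section 4.0) to event-monitoring forms every 6 months until progression (Section 18.1).

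**Working it through.** The plan gives no figure to reproduce here, so the check is a row-by-row comparison. It covers each Table 8.2 row that names a restart dose, for a first event in a patient on 45 mg. One level down from 45 mg is 30 mg (Section 8.1).

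| Table 8.2 rows | Dose, table | Dose, 8.3 | Recovery, table | Recovery, 8.3 |
|---|---|---|---|---|
| Neutrophils; platelets; amylase without radiographic findings; pancreatitis ≥ Grade 2; LV dysfunction ≥ Grade 3; rash ≥ Grade 2 (6 rows) | 45 mg | 30 mg | ≤ Grade 1 | ≤ Grade 1 or baseline* |
| Amylase with findings or Grade 4; ALT/AST; pancreatitis ≥ Grade 3; rash ≥ Grade 3; hypertension Grade 2–3; hypertension ≥ Grade 4 (6 rows) | 30 mg | 30 mg | ≤ Grade 1 | ≤ Grade 1 or baseline |
| Other Non-Hematologic events ≥ Grade 3 (1 row) | next lower level, 30 mg | 30 mg | ≤ Grade 2 | ≤ Grade 1 or baseline |

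*For neutrophils and platelets Section 8.3 uses counts (1500 and 75,000 per µL). The documents do not reproduce the CTCAE cut-points, so these were not compared with Grade 1.

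Counts: 6 + 6 + 1 = 13 rows. Dose conflicts in 6 and agrees in 7. Recovery grade clearly conflicts in 1. No row has both conflicts. At recurrence on 45 mg or 30 mg the six conflicting rows also step down one level, so the dose conflict belongs to the first event.

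**(a) Restart dose.** Take a first Grade 3 neutropenia that keeps the drug off for 7 days.
- Off from Day 8: 8 + 7 = Day 15, within the cycle. The table gives 45 mg, and the Section 8.3 reduction is not triggered.
- Off from Day 22: 22 + 7 = Day 29, which is the next Day 1. The table gives 45 mg; Section 8.3 gives 30 mg.

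The difference is 45 − 30 = 15 mg a day, one third of the starting dose.

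**(b) Recovery grade.** Take a ponatinib-related Grade 3 event in the Other Non-Hematologic row, with drug off from Day 8. It improves to Grade 2 by Day 15, and the table allows restart at 30 mg. If it is still Grade 2 and above baseline on Day 29, the table gives no reason to stop. Section 8.3 nevertheless withholds the new cycle. If nothing changes by Day 29 + 28 = Day 57, counted from the start of the earlier cycle, the patient is removed. If improvement to Grade 2 comes only at or after the scheduled Day 1, the two texts conflict directly on whether the drug may restart.

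**(c) Hypertension on Day 1, the weaker case.** For related Grade 2 or 3 hypertension newly found on a scheduled Day 1, Table 8.2 puts blood-pressure treatment before any interruption or reduction. Section 8.3 delays the cycle and then lowers the dose. Once an interruption is reached, both give 30 mg, so the conflict is over the order of steps.

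**The case against.** The best reply is that the two texts do different jobs. Table 8.2 is headed as applying to interval adverse events, and its example of an omission runs from Day 8 to Day 15 of one cycle. Section 8.3 deals only with starting a new cycle, and its trigger for reduction is in bold. On that reading it is an added rule for interruptions that cross a cycle boundary, and dependence on cycle day is a design choice. This reading is possible, but the protocol does not state it. The definition of Omit points the other way, to recovery as Table 8.2 sets it. A site could defend either dose.

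Three mitigating points stand. A note under Table 8.2 lets the investigator raise the dose again, one level at a time, after a reduced cycle with no further event above Grade 2, so the difference in (a) may later be reversed. The baseline-severity clause exempts some patients in (b) and (c). The hypertension row is worded as a recommendation with room for discretion.

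Stronger readings are tempting, and the documents do not support them:
- A reader might infer that dose and recovery grade both conflict whenever an interruption reaches Day 1. The table above shows otherwise.
- A reader might put a frequency on the problem. With uniform onset and assumed interruptions of 7, 14 or 21 days, 7/28, 14/28 and 21/28 give 25%, 50% and 75% reaching the next Day 1. Those durations are not in the documents, and the shares count where both texts apply, including rows that agree.
- Section 9.5 reports treatment-emergent hypertension in 300/449 (67%). That covers any such hypertension, not related Grade 2–3 events first seen on a Day 1.
- A reader might infer that safety results by dose level could not be interpreted. No such analysis is planned: Section 16.324 tabulates the maximum grade per patient.

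**Conclusion.** The contradiction is real but confined to particular rows. It affects first-event restart dose in 6 of 13 rows, by one dose level, and recovery grade in 1 of 13, where it can lead to removal from treatment. Hypertension first found on Day 1 is a softer third case. No passage states precedence.

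The row counts assume a first event on 45 mg. On a lower dose, the rows that name a fixed restart dose in mg could conflict with Section 8.3 more often.

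A reader might go on to infer that the trial's conclusion is at risk, because the final boundary is 2 versus 3 successes in 27 (Section 16.212). One reclassified patient at that boundary would matter. But only case (b) leads to removal under one text and not the other. It requires a related event that stays at Grade 2, above baseline, until 28 days past Day 1, in a patient whose benefit is not yet established. The documents give no frequency for that, so no effect on the decision can be claimed. The case for change rests on the conflicting instructions themselves.

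**What to change.** Reconcile Section 8.3 with Table 8.2, and state which text governs:
1. the restart dose in the six rows that resume at 45 mg, when the interruption reaches the next Day 1 or the event is first found on Day 1;
2. the recovery grade for the Other Non-Hematologic events row, including a patient already restarted mid-cycle at Grade 2;
3. Grade 2 or 3 hypertension first found on a scheduled Day 1.

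Which dose, grade or rule applies, and whether it should depend on cycle day, is the sponsor's clinical decision. The cost is wording in Section 8, with no added visits, tests or patients.

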3.2 Exclusion Criteria

- 3.21 Any of the following because this study involves an investigational agent whose genotoxic, mutagenic and teratogenic effects on the developing fetus and newborn are unknown:
- Pregnant women
 - Nursing women
 - Men or women of childbearing potential who are unwilling to employ adequate contraception
- 3.22 Co-morbid systemic illnesses or other severe concurrent disease which, in the judgment of the investigator, would make the patient inappropriate for entry into

this study or interfere significantly with the proper assessment of safety and toxicity of the prescribed regimens.

- 3.23 Immunocompromised patients and patients known to be HIV positive and currently receiving antiretroviral therapy. NOTE: Patients with a known history of HIV infection are not eligible for this trial.
- 3.24 Uncontrolled intercurrent illness including, but not limited to, ongoing or active infection, symptomatic congestive heart failure, unstable angina pectoris, cardiac arrhythmia, or psychiatric illness/social situations that would limit compliance with study requirements.
- 3.25 Receiving any other investigational agent which would be considered as a treatment for the primary neoplasm.
- 3.26 Prior systemic chemotherapy, radiation therapy or major surgery \leq 30 days prior to registration.
- 3.27 Concurrent use of any other approved or investigational anticancer agents, including hormonal agents
- 3.28 Prior nitrosourea or mitomycin C \leq 6 weeks prior to registration.
- 3.29a Patients with gastrointestinal comorbidities that would affect intake or absorption of ponatinib
- 3.29b Untreated or progressive brain metastases
- 3.29c Prior treatment with or allergic reactions attributed to compounds of similar chemical or biologic composition to ponatinib
- 3.29d Clinically uncontrolled hypertension (diastolic blood pressure >90 mm Hg; systolic >140 mm Hg). NOTE: Patients with hypertension should be undergoing treatment at study entry for blood pressure control.
- 3.29e Previous or concurrent malignancy except adequately treated basal or squamous cell skin cancer, in situ carcinoma of the cervix, or other solid tumor treated curatively and without evidence of recurrence for at least 5 years
- 3.29f History of significant bleeding disorder unrelated to cancer
- 3.29g History of acute pancreatitis within 1 year prior to registration, chronic pancreatitis, alcohol abuse or uncontrolled hypertriglyceridemia (triglycerides >450 mg/dL)

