4.0 Test Schedule

Cycle = 28 days

Tests and procedures	Active Monitoring Phase						
	≤14 days prior to registration	Cycle 1 Day 1 (± 2 days) prior to treatment	Cycle 1 Days 8, 15, 22 prior to treatment	Cycle 2 and beyond Day 1 (± 2 days) prior to treatment	Q 8 weeks from Cycle 1 Day 1 (± 5 days)	Every 3 Cycles starting at end of Cycle 3 (± 5 days)	End of treatment
History and exam, wt, ECOG	X			X			X
Height, Child Pugh score	X						
Vitals ³	X	X	X	X			X
Hematology group WBC, ANC, Hgb, PLT	X	X	X	X			X
Chemistry group Sodium, potassium, chloride, bicarbonate, total protein, albumin, calcium, glucose, BUN, total bilirubin, creatinine, alkaline phosphatase, SGOT (AST), SGPT (ALT)	X	X		X			X
Amylase ^R	X	X	X	X			
Lipase ^R	X	X	X	X			
CA19-9		X		X ⁵			
EKG ^R	X					X	
Echocardiogram	X			X ¹⁰			
Tumor measurement and Imaging (CT or MRI as clinically)	X ¹				X ²		

indicated)							
Pregnancy test	X ⁴						
Patient questionnaire booklet	X ⁹			X ⁹			
Adverse event assessment	X		X	X			
Research Archival Tissue (optional)	X ⁸						
Research Tissue Biopsy (optional)				X ^{7,R}			X ⁶
Research blood samples (Optional)	X			X			X

1. Imaging studies such as CT scans, and MRIs can be performed ≤ 28 days prior to registration. Use same imaging throughout the study. Assessment by physical exam should be done ≤ 14 days prior to registration.
 2. Tumor assessment must be performed at least every 8 weeks. Tumor assessment should be performed at any time during the treatment cycle that disease progression is clinically suspected so that patient can go off treatment and receive other therapy.
 3. Includes weight, blood pressure, pulse and temperature
 4. Women of childbearing potential only. Must be done ≤ 7 days prior to registration.
 5. Only to be collected if $> \text{ULN}$ on Cycle 1 Day 1
 6. If patient has experienced disease progression and at such time a standard of care biopsy is ordered by the treating physician, waste specimen will be collected, fresh frozen and stored for future correlative studies. Perform only if archival specimen was available.
 7. Perform only if archival specimen was available.
 8. Archival FFPE and/or fresh frozen tissue collected in setting of standard of care procedures.
 9. Patient questionnaire booklet must be used; copies are not acceptable for this submission. Booklet should be completed by patient prior to review of treatment response and discussions of patient's general health since last treatment evaluation.

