18.0 Records and Data Collection Procedures

18.1 Submission Timetable

Initial Material(s)

CRF	Active-Monitoring Phase (Compliance with Test Schedule Section 4.0)
On-Study	≤14 days after registration
Adverse Event - Baseline	
RECIST Measurement – Baseline	
Concomitant Medication - Baseline	
Hematology Laboratory	
Chemistry Laboratory	
Other Laboratory	
Patient Questionnaire Booklet ¹	
Booklet Compliance ²	
OP and Path Reports (see Section 17.0)	
Research Blood Submission	≤30 days after registration
Research Tissue Submission	
End of Active Treatment/Cancel Notification	Submit ≤2 weeks after registration if withdrawal/refusal occurs prior to beginning protocol therapy

1. Patient questionnaire booklet **must** be used; copies are not acceptable for this submission.
2. This form must be completed only if the patient questionnaire booklet contains absolutely NO patient provided assessment information.

Test Schedule Material(s)

CRF	Active-Monitoring Phase (Compliance with Test Schedule Section 4.0)
	At each evaluation during treatment
Evaluation/Treatment	X ¹
Adverse Event	X

CRF	Active-Monitoring Phase (Compliance with Test Schedule Section 4.0)
	At each evaluation during treatment
RECIST Measurement	X
Concomitant Medication	X
Other Laboratory	X (see Section 4.0)
Hematology Laboratory	X (see Section 4.0)
Chemistry Laboratory	X (see Section 4.0)
Research Tissue Submission	X (see Section 17.0)
Research Blood Submission	X (see Section 14.0)
Patient Questionnaire Booklet	X ²
Booklet Compliance	X ³
End of Active Treatment/Cancel Notification	X
Notification Form – Grade 4 or 5 Non-AER Reportable Events/Hospitalization	At each occurrence (see Section 10.0)
ADR/AER	At each occurrence (see Section 10.0)

1. Complete at each evaluation during Active Treatment (see Section 4.0).
2. Patient questionnaire booklet **must** be used; copies are not acceptable for this submission. To be completed prior to treatment every cycle.
3. This form must be completed only if the patient questionnaire booklet contains absolutely NO patient provided assessment information.

Follow-up Material(s)

CRF	Event Monitoring Phase ¹				
	q. 6 months until PD	At PD	After PD q. 6 mos.	Death	New Primary
Event Monitoring	X ²	X ²	X	X	At each occurrence

1. If a patient is still alive 2 years after registration, no further follow-up is required.
2. Submit copy of documentation of response or progression to the MCCC Operations Office, Attention: XXXXXXXXXX.

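### The test schedule has no lipase draw between Day 29 and Day 57, although Section 8.42 asks for one every 2 weeks in that period

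*Combined protocol and SAP*

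**What the plan says.** Section 8.42 (Pancreatitis) sets the frequency: "Check serum lipase every 2 weeks for the first 2 months and then monthly thereafter or as clinically indicated". It reports treatment-emergent lipase elevation in 41% of patients and clinical pancreatitis in 6% (28/449). It also directs: "In cases where lipase elevations are accompanied by abdominal symptoms, interrupt treatment with Iclusig and evaluate patients for pancreatitis".

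The lipase row of Section 4.0 is marked in four columns: screening, Cycle 1 Day 1, "Cycle 1 Days 8, 15, 22 prior to treatment", and "Cycle 2 and beyond Day 1 (± 2 days) prior to treatment". Its only superscript is the one for research funding. None of the numbered footnotes adds a lipase draw. The amylase row is marked in the same four columns.

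Section 7.2 sets the visit interval: "the patient must return to the consenting institution for evaluation at least every 28 days (+/- 2 days) during treatment". No mid-cycle visit is scheduled after Cycle 1.

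**The concern.** The frequency in Section 8.42 and the calendar in Section 4.0 agree except in Cycle 2. Section 8.42 puts the whole of the first 2 months on a two-weekly interval, whereas Section 4.0 moves to one draw per cycle as soon as Cycle 2 starts. A site can meet every entry in the table and still not do what Section 8.42 asks.

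At stake is one routine check per patient still on treatment at Day 43. It matters mainly for patients without symptoms, because symptoms would prompt testing anyway. Section 8.42 allows that a dose interruption or reduction may be needed, so a routine result can change dosing. Sites that work from Section 8.42 would also monitor Cycle 2 differently from sites that work from the table.

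**Working it through.** **Inputs.** Cycle length of 28 days, lipase row and ±2-day window on Day 1 visits: Section 4.0. Return interval of 28 ±2 days: Section 7.2. Two-weekly frequency for 2 months: Section 8.42. Maximum accrual of 30: Section 16.22.

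**Calendar.** Cycle c Day d falls on study day 28(c − 1) + d.
- Cycle 2 Day 1 = 28 + 1 = Day 29
- Cycle 2 Day 15 = 28 + 15 = Day 43
- Cycle 3 Day 1 = 56 + 1 = Day 57

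**Side by side, Day 1 to Day 57.**

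| Source | Lipase days | Gaps (days) |
|---|---|---|
| Section 8.42 | 1, 15, 29, 43, 57 | 14, 14, 14, 14 |
| Section 4.0 | 1, 8, 15, 22, 29, 57 | 7, 7, 7, 7, 28 |

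Section 4.0 has 5 draws after Day 1 against 4 under Section 8.42, because Cycle 1 is weekly. It nevertheless covers only 3 of the 4 two-weekly dates (15, 29 and 57). Day 43 is the only one missing, and the nearest scheduled draws are 14 days away on either side. The next two-weekly date, Day 71, lies beyond 2 months (about 61 days), so no other date is in question. From Day 57 the table is monthly, as Section 8.42 asks.

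**Width of the gap with visit windows.**
- Section 7.2 reading, each visit counted from the one before: 28 − 2 = 26 to 28 + 2 = 30 days.
- Fixed calendar, both windows anchored to Cycle 1 Day 1: Day 29 becomes 27 to 31 and Day 57 becomes 55 to 59. The gap is then 55 − 31 = 24 to 59 − 27 = 32 days.

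**After adding Day 43.** The nominal gaps become 7, 7, 7, 7, 14, 14. On the fixed calendar, with ±2 days on the new draw (Days 41 to 45), each of the last two gaps runs from 41 − 31 = 10 to 45 − 27 = 18 days; 55 − 45 and 59 − 41 give the same limits.

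**Cost ceiling.** 1 draw × 30 patients = 30 draws.

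**What cannot be computed.** The documents give no onset times for lipase elevation, so the number of detections delayed by the longer gap cannot be derived.

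**The case against.** The best defence is that Section 4.0 is the study-specific schedule, while Section 8.42 sits under additional guidance and reads like general product information. It even advises extra monitoring for patients whom the exclusion on "History of acute pancreatitis within 1 year prior to registration, chronic pancreatitis, alcohol abuse or uncontrolled hypertriglyceridemia" largely removes. The table tests more often than Section 8.42 asks in Cycle 1. Section 3.16 caps baseline lipase and amylase, and unscheduled testing is allowed. Table 8.2 has explicit dose rules for amylase and none for lipase, so a raised lipase without symptoms leads only to a discretionary response. Rewording Section 8.42 to match the table would also remove the mismatch.

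Much of this stands, and it is why the point is minor. It does not remove the gap. The lipase sentence is an instruction with a stated frequency, whereas the sentence that follows it is worded as discretion. Table 8.2 itself sends investigators to Sections 8.41 through 8.47. Permission to test when indicated does not schedule a routine test. Weekly draws in Cycle 1 give no information about Days 30 to 56, and amylase does not fill the hole because it has the same gap. Rewording Section 8.42 would settle the text by giving up a check that the protocol already asks for.

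Two stronger readings are tempting. A reader might infer from the Section 18.1 column header "Active-Monitoring Phase (Compliance with Test Schedule Section 4.0" that sites are held to the table and would therefore skip Day 43. The header only labels a phase in a form-submission timetable; it does not limit testing to Section 4.0 or show what sites would do. A reader might also take 32 days as the longest permitted gap. That figure needs both windows anchored to Cycle 1 Day 1, and it exceeds the 30 days that Section 7.2 allows between visits.

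**Conclusion.** The mismatch is real and confined to Cycle 2. One two-weekly lipase check, Day 43, is missing from the schedule. The gap is 28 days nominally and 26 to 30 days under Section 7.2, against 14 in Section 8.42.

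It is an omission rather than a contradiction, since a site that adds the draw satisfies both sections. A reader might infer from the 41% and 6% figures that pancreatitis would be missed. The documents do not support that: they give no timing, and Section 8.42 already requires interruption and evaluation when raised lipase comes with abdominal symptoms. Lipase is not an endpoint, so the primary analysis, sample size and error rates are untouched.

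The result assumes 28-day cycles without delay. Under Section 8.3 a delayed cycle restarts its day count when therapy resumes and brings at least weekly evaluation in the meantime. The change is worth making because it is cheap and delivers what the protocol already instructs.

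**What to change.** Add a lipase draw at Cycle 2 Day 15 (Day 43, ±2 days) to Section 4.0, with a footnote that a local laboratory draw is acceptable. Run amylase on the same sample, because it has the same gap and is the enzyme with explicit dose rules in Table 8.2. The longest nominal interval in the first 2 months then becomes 14 days.

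The cost is at most 30 extra draws, fewer if patients leave treatment before Day 43. Section 19.2 already lists both enzymes as research funded. No Cycle 2 Day 15 visit exists, so each draw may mean a trip to a local laboratory. Some raised values in patients without symptoms will lead to dose interruptions or reductions that would not otherwise have happened at that time.
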